## 1. INTRODUCTION

The purpose of the Lung Institute is to collect and process a patient's own stem cells and platelet rich plasma (PRP) and deliver them back to the patient same-day through an intravenous catheter and sometimes by nebulizer. Lung Institute's treatment is limited to self-funded patients with chronic lung diseases – chronic obstructive pulmonary disease (COPD) and interstitial lung disease (ILD). The patient's stem cells and platelet rich plasma are collected through venous, adipose or bone marrow harvesting techniques. After the stem cells and platelet rich plasma have been isolated they are administered back to the patient. An inhaled antioxidant, glutathione, is administered during treatment to help mobilize lung secretions.

Researchers have demonstrated that using autologous stem cells (those derived from the patient) with minimal manipulation is safe and effective to promote the healing of lung tissue affected by COPD and ILD. The administration of glutathione to mobilize secretions in the lung has been determined a safe and effective addition to treatment (Jones, 2011).

In a pilot study conducted by [name] at Lung Institute Nashville, after following approximately 100 treated patients, [name] discovered that within three months of treatment, 84 percent of patients reported improvement in their quality of life (Coleman, 2016). For millions of people suffering from COPD, a natural decline in pulmonary health is a harsh reality. Based on these results, stem cell therapy gives promise to improving their quality of life and slowing down the progression of disease.

At this time, autologous stem cell collection and administration is not commercially available and therefore is considered an investigational agent under the standards of the Texas Medical Board.

Lung Institute's collection and administration of stem cells as investigational agents in the state of Texas is part of a systematic program monitored under the strict oversight of Lung Institute's business associate and medical management services company, Regenerative Medical Solutions (RMS). Lung Institute and RMS are committed to the highest level of concern and caution for the welfare, safety and comfort of the patient to whom the cell therapy treatment is administered.

The hypothesized outcomes of Lung Institute therapy are safety and minimization of adverse events, a perceived improvement in the patient's lung condition (to be determined by their ability to be more physically active; walking greater distances with or without oxygen and improved quality of life scales), an improvement in their FEV1 5-10% or more, the ability to reduce their use of oxygen and possibly to stop it., the ability to function well without the use of rescue inhalers, reduction or ceasing of secondary pulmonary infections, reduction in emergency room visits and hospitalizations related to their disease, and an improvement in their six minute walk test.

**Research Protocol**  
**Lung Institute Dallas**

## 2. BACKGROUND

Currently, literature on the outcomes of autologous stem cell treatment for COPD is lacking.

- A white paper released by the Medical Director at Lung Institute Nashville found an 84 percent response rate in improved quality of life indicators among 100 patients followed after treatment (Coleman, 2016).

- The Lung Institute is a leader in the field of regenerative medicine with strong clinical protocols and a solid understanding of the safety and efficacy of stem cell treatment for chronic lung disease.

## **2a. Situating the Researcher**

[name] is a doctorally-prepared Family Nurse Practitioner certified by the American Nurses Credentialing Center and licensed to practice in the state of Texas. A member of the Southern Nursing Research Association, [name] has experience designing and conducting qualitative and quantitative research and mixed-methods studies. Her doctoral dissertation was a qualitative study involving a marginalized population of drug-addicted women ([name], 2013). She has also done pilot work on a population of incarcerated women using quantitative methods. [name] has a current manuscript pending review on using the interpretive phenomenological inquiry method for qualitative research. [name] is well-experienced in the protection of human research subjects. She is an expert in the promoting rigor in qualitative research design and situating its importance in medical research.

[name] is a nationally certified and practicing Family Nurse Practitioner. In addition to her research role, [name] will be the primary clinician at the research site, providing physical assessments, reviewing patient medical records and formulating the patient plan of care. Because each patient of the Lung Institute is treated using the same protocols (there are no control groups), this minimizes the conflict of interest, randomization and blinding that must occur with experimental studies.

## **3. AIM(S) OF STUDY**

Through the collection of qualitative and quantitative data, Lung Institute aims to explore and describe the safety and efficacy of autologous stem cell treatment for chronic lung disease with dissemination to the public and to the medical community for the advancement of regenerative medicine. The study aims to confirm the safety of autologous cell therapy, explore the effect of autologous cell therapy treatment on pulmonary function, and to describe the anecdotal quality of life changes of patients following treatment using both quantitative and qualitative measures.

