## **4. RESEARCH QUESTIONS**

The research questions to be informed by this investigation are as follows:

1. Is the collection and administration of autologous stem cells for the treatment of chronic lung disease safe?
2. Does treatment with autologous stem cells for chronic lung disease improve measurements of pulmonary function (specifically FEV1)?
3. Does treatment with autologous stem cells for chronic lung disease improve the patient's perceived quality of life?

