**Research Protocol**  
**Lung Institute Dallas**

### **5b. Secondary Hypothesis/Quantitative Arm**

There will be no adverse events reported following autologous stem cell treatment for chronic lung disease.

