### 9b. Exclusion criteria

Exclusions from **ALL** Procedures:

- Populations
  - Inability to give informed consent (a diminished understanding or comprehension);
  - Inability to travel to Outpatient Facility;
  - Pregnant women;
  - Prisoners; and
  - Children, under the age of 16 years old
- Active Smoker - Active smoking prevalence has been estimated at:
  - Nationally: 17.8 %
  - Texas: 15.9 %
  - Dallas County: 15.3 %
  - Denton County: 10.1 %
  - Collin County: 9.7 %
- Currently diagnosed with cancer or have had cancer within the past 5 years.
  - Current cancer prevalence is estimated by the National Cancer Institute at 3.7% for males in Texas and 3.9% for females in Texas. National cancer cases were estimated in 2010 to be 13,772,000 nationally for a prevalence rate of 4.5% of the estimated national population of 309,300,000.
- Identification of new nodules/masses per chest x-ray/CT scan report that have not been noted as stable.
  - Documentation of stability must be received for confirmation prior to treatment.
- Active Infection (pulmonary or other);
- Active Tuberculosis
- A History of Recent Hospitalization (requiring mechanical ventilation in a period of one month before treatment);
- End Stage Kidney Failure;
- Acute Heart Failure; and/or
- Other Condition(s) the Provider or Principal Investigator feels would interfere with treatment protocols.

Rev\_2/5/16 Page 4 of 10

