**Research Protocol**  
**Lung Institute Dallas**

## 11. STUDY PROCEDURES

Informed Consent Form is obtained. Consent form must be complete, signed, and dated without forgeries or alterations. Information should be delivered in a manner in which the Patient and/or the patient's legal representative could reasonably be expected to understand.

A review of the patient's medical record will be conducted to approve for treatment. Approved treatment plans will be documented in the patient's electronic medical record. Medical records obtained from external providers will be kept in the patient's medical record and must include recent laboratory data, results of any outside office notes, chest x-ray results and any relevant information as required per treatment inclusions and exclusions protocol.

Prior to Bone Marrow aspiration, Adipose extraction, and Venous stem cell administration, the clinician will perform a physical assessment. Attached are the following Standard Operating Procedures (SOPs) for each type of cell therapy that Lung Institute provides to qualified candidates:

- Venous Procedure
- Adipose Extraction Procedure
- Bone Marrow Aspirate Procedure

Patient follow-up may be conducted at the Lung Institute facility or may be completed by telephone at 2 weeks, 3 months and 6 months post-treatment to measure adverse events and quality of life. Patient participation in these phone calls is voluntary. Data collected at these time points will be entered into password-protected database for data management and reporting. Patients will be issued a journal during their treatment to record quality of life indicators from the time they are discharged from the clinic until they are called for follow-up. This allows the patients to better recall how they felt/are feeling to better communicate progress during follow-up appointments/calls.

Patients will have pulmonary function testing 6 months post-treatment. This will be done at the Lung Institute facility, or by their primary care physician, or pulmonologist.

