- **Transfers of undiagnosed cancer** – There is a risk that undiagnosed cancer in the area where the stem cells are harvested may be transferred to the recipients area of transplantation. To minimize risks, stem cells will not be altered in any way, thereby reducing the risk of tumor induction by carcinogens.

Rev\_2/5/16 Page 8 of 10

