### Research Protocol Lung Institute Dallas

- **Administration of incorrect stem cells** – The stem cells administered are the recipients own stem cells. There is a low risk of administration errors. Materials are clearly marked before they leave the procedure room, eliminating the risk of a recipient receiving someone else's stem cells in error.
- **Unintended differentiation** - The unintended differentiation of stem cells was found in a single study in which extensive intra-myocardial calcification after unselected bone-marrow cells transplantation was seen in the peri-infarct and infarct areas in rats. Though a low risk, unintended differentiation could occur in areas of stem cell implantation.

The following lists the potential benefits of treatment:

- **Increased Activity** - Ability to be more physically active; walking greater distances.
- **PFT** - Improvement in their FEV1 5-10% or more.
- **Oxygen** - Ability to reduce their use of oxygen and possibly to stop it.
- **Reduction in Medications** - Ability to function well without the use of their bronchodilator inhalers and Prednisone.
- **Increased Pulmonary Health** - Reduction or ceasing of secondary pulmonary infections

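### Section 3 sets out to confirm safety, but an uncontrolled study of about 200 patients with scheduled follow-up to six months can only describe reported adverse events

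*Combined protocol and SAP*

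**What the plan says.** Section 3 words the safety aim in two ways. One sentence reads "Lung Institute aims to explore and describe the safety and efficacy of autologous stem cell treatment for chronic lung disease"; the next reads "The study aims to confirm the safety of autologous cell therapy". Section 4, question 1 asks "Is the collection and administration of autologous stem cells for the treatment of chronic lung disease safe", without a time horizon or type of event. Section 5b sets the safety hypothesis: "There will be no adverse events reported following autologous stem cell treatment for chronic lung disease". Section 12b closes by saying that the study will inform the public and the medical community about safety and efficacy, again without a limit.

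On the design, section 2a says there is no control group, section 6 says safety is analysed descriptively and reported separately, and section 12a anticipates 200 patients. Section 11 allows follow-up at the facility or "by telephone at 2 weeks, 3 months and 6 months post-treatment to measure adverse events and quality of life", and makes taking part in the calls voluntary. Policy CL-005, section H, provides two call attempts at each contact. At six months it advises a visit for an evaluation, labs, pulmonary function, oximetry and a walk test. If the patient cannot return, a local physician's examination with the same tests is advised. No imaging is listed and no later contact is planned.

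Section 13 names among the risks that "undiagnosed cancer in the area where the stem cells are harvested may be transferred to the recipients area of transplantation". It also says: "Though a low risk, unintended differentiation could occur in areas of stem cell implantation".

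**The concern.** To confirm safety is to claim that harms of concern have been looked for and bounded. Here nothing in the plan states what size of risk would be ruled out, over what period, or against what comparison. The section 5b hypothesis is met when nothing is reported, so a patient who does not answer the phone, or whose event shows after the last contact, counts in its favour.

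Two of the plan's own named risks have no assessment aimed at them after treatment. Before treatment, by contrast, a chest X-ray or CT is among the required records (step 2 of the Venous and Bone Marrow SOPs), and section 9b excludes new nodules not shown to be stable.

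The results are meant for the public, the treatment is fee-for-service (section 14), and section 2 concedes that outcome literature in COPD is lacking. A report that safety was confirmed could therefore carry weight with prospective patients that the data would not support.

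**Working it through.** **The plan's own figure.** The 200 in section 12a comes with no event rate, margin, confidence level or allowance for loss. It can be neither reproduced nor called wrong. The check is what 200 patients could show about any one type of event if no case is reported.

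**Inputs.** n = 200 (section 12a); last scheduled contact at six months (section 11; CL-005, section H). Response rates and time to detection are not given, so the values used for them below are assumptions.

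**1. Best case: all 200 followed, every case visible by six months, zero seen.**

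- One-sided 95% upper limit: 1 − 0.05^(1/n) = 1 − 0.05^(1/200) = 1.49%.
- Two-sided 95% interval, upper end: 1 − 0.025^(1/200) = 1.83%.

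**2. Chance of seeing at least one case in 200,** 1 − (1 − p)^200:

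- true risk 0.1%: 18%
- true risk 0.5%: 63%
- true risk 1%: 87%

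**3. Incomplete response (assumed numbers followed).** One-sided upper limit with zero events, by the formula in step 1:

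- 160 followed: 1.85%
- 140 followed: 2.12%
- 100 followed: 2.95%

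**4. Late onset (assumed).** Let time to detection be exponential with median m years, with all 200 followed. The share of eventual cases visible by six months is s = 1 − 2^(−0.5/m). The chance of seeing any case at a true eventual risk of 1% is 1 − (1 − 0.01s)^200. The upper limit on the eventual risk after zero events is 1.49%/s.

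| Median m (years) | Share visible, s | Chance of any case at 1% risk | Upper limit on eventual risk |
|---|---|---|---|
| 0.5 | 50% | 63% | 3.0% |
| 1 | 29% | 44% | 5.1% |
| 2 | 16% | 27% | 9.3% |
| 5 | 7% | 12.5% | 22% |

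For the first row: s = 1 − 2^(−1) = 0.50, and 1.487%/0.50 = 2.97%. The table shows sensitivity only; the documents give no latency for either named risk.

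**5. Wording against design.** The describing sentence in section 3 fits the descriptive analysis in section 6. The confirming sentence, question 1 and the section 12b statement do not, because no comparison, margin or time limit goes with them.

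**The case against.** The strongest reply is that the plan as a whole is descriptive. The confirming phrase follows a sentence about exploring and describing, section 4 says its questions are to be informed by the study rather than settled, and section 6 plans only a descriptive safety report. That is true, and it is why the repair is small. It does not remove the phrase, which contradicts its neighbour, or the unlimited wording elsewhere.

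A second reply is that follow-up is better than a list of tests suggests. The six-month visit includes a clinical evaluation or examination, and section 11 has all adverse events reported to the principal investigator with no stated cut-off; only the scheduled contacts end. This stands. An early or clinically evident case could be found, and a later one could be volunteered.

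A third is that most entries in section 13, such as fever, pain, infection and anaemia, relate to the harvest or procedure, for which six months is a relevant period. The list restates consent-form risks rather than study endpoints, and the case for unintended differentiation rests on one study in rats. This also stands, and it supports a claim limited to six months.

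Finally, duration may not be the main limit: size, voluntary contact and the lack of a control group matter too. Agreed. Step 2 of the working shows that sample size alone leaves rare events largely undetectable, even with no delay in onset.

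**Conclusion.** The point holds as an overstatement of what the design can conclude. The study can describe adverse events reported through six months. It cannot confirm safety or exclude rare or later events, among them cancer transfer and unintended differentiation. With zero events in 200 fully followed patients the one-sided 95% upper limit is about 1.5%; this assumes complete follow-up and no late onset, and it rises if either fails.

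A reader might infer three stronger things that the documents do not support.

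- *That six months is only a tenth of the period over which cancer would appear.* The exclusion "Currently diagnosed with cancer or have had cancer within the past 5 years" is a look-back at entry. CL-005 lets the provider make case-by-case exceptions for non-aggressive or inactive disease. It is not a detection window, so dividing six months by five years measures nothing here.
- *That six months cannot assess these risks at all.* No latency or detection method is given, and an early case could be reported. Failure to exclude is the accurate statement.
- *That tumour induction is a third listed risk.* Section 13 mentions it only in the sentence on how the cancer-transfer risk is reduced.

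**What to change.** - **Section 3:** replace the confirming phrase with an aim to describe adverse events reported through six months, which also brings the two sentences into agreement.
- **Section 4, question 1, and the closing statement of section 12b:** limit the safety wording in the same way.
- **Safety analysis (sections 6 and 12b):** report the proportion of patients with each type of event, with exact binomial confidence intervals including those for zero counts. Give the number of patients actually followed as the denominator.
- **Limitation statement, in the protocol and any report:** absence of reports does not exclude cancer transfer, unintended differentiation or other late events.

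The change is to wording and to a few lines of the safety table. No procedure or assessment changes. The number followed should be obtainable from the follow-up database described in section 11. The downside for the sponsor is a less favourable safety claim.

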## **4. RESEARCH QUESTIONS**

The research questions to be informed by this investigation are as follows:

1. Is the collection and administration of autologous stem cells for the treatment of chronic lung disease safe?
2. Does treatment with autologous stem cells for chronic lung disease improve measurements of pulmonary function (specifically FEV1)?
3. Does treatment with autologous stem cells for chronic lung disease improve the patient's perceived quality of life?

## **5. HYPOTHESES**

### **5a. Primary Hypothesis/Quantitative Arm**

Null hypothesis: Following autologous stem cell treatment for chronic lung disease, patients will have no improvement in pulmonary function (measured by FEV1) at six months

Alternative hypothesis: Following autologous stem cell treatment for chronic lung disease, patients will have an increase in pulmonary function (measured by FEV1) of 5 to 10% or more

Rev\_2/5/16 Page 2 of 10

**Research Protocol**  
**Lung Institute Dallas**

### **5b. Secondary Hypothesis/Quantitative Arm**

There will be no adverse events reported following autologous stem cell treatment for chronic lung disease.

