## 6. STUDY DESIGN

This study uses a concurrent mixed-methods approach to collect and analyze both qualitative and quantitative data. The *quantitative* arm will use a non-experimental, descriptive approach to measure and analyze pre- and post-stem cell treatment pulmonary function test results of treated patients. Measurement of the occurrence of adverse events will also be part of the quantitative arm.

Pre-treatment pulmonary function test results (measured by FEV1) will be compared with a six-month post-treatment pulmonary function test result (FEV1) for each patient. The aim of this method is to generalize an improvement in pulmonary function (measured by FEV1) among the general population of all individuals treated by autologous cell therapy for chronic lung disease.

The *qualitative* arm of the study uses an interpretive phenomenological approach to collect and analyze pre- and post- cell therapy anecdotal data regarding perceived quality of life among treated patients. Phenomenological research involves investigating the lived experience.

Qualitative research has several assumptions (D. Nicholls, 2009; Ritchie & Lewis, 2003). Primarily, there is no predetermined theoretical framework- rather the theory, if any, is derived from the data. Secondly, qualitative research is context-driven. Finally, qualitative researchers focus on the *emic* perspective that concerns itself with the view, perspectives and descriptions of others.

This study uses an *interpretive phenomenological analysis* (IPA) approach throughout the study from planning to data collection to analysis. This methodology is used to illuminate each participant's variation of the same general phenomenon (in this case, COPD) (Reissman, 2008; Ritchie & Lewis, 2003).

Data from both arms of the study will be combined following data collection for analysis, discussion and presentation. Safety data on adverse outcomes will be tracked and reported separately as a descriptive, quantitative analysis.

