## 10. STUDY OUTCOMES

The anticipated outcomes of this study are a minimization of adverse events, an improvement in pulmonary function testing (measured by FEV1), and an improvement in self-reported quality of life indicators.

Rev\_2/5/16 Page 5 of 10

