### **12b. Statistical methods**

For the quantitative, descriptive arm of this study, sample characteristics will be collected to include age, sex and diagnosis. Pre- and post-treatment FEV1 measurements will be collected on each patient and evaluated by simple measures of central tendency (mean, median and mode). Sufficient descriptive data will be collected and reported to encourage replication of our study.

For the qualitative, anecdotal arm of the study, Lung Institute utilizes CCQ, the Clinical COPD Questionnaire to document patient's perceptions on improved quality of life. The information will be collected and interpreted by evaluating for common themes within the anecdotes. As a note regarding the rigor of qualitative research: is important in qualitative research to ensure that the study is credible and trustworthy (Smith, Flowers and Larkin, 2009). A number of guidelines for assessing this quality look toward establishing credibility. Psychologist Lucy Yardley's work in 2000 provides the principles for assessing the quality of qualitative research and how the interpretive phenomenological method can address them. First, the study must provide good *sensitivity to context*. In this study, the immersion in the clinic through field experience, the existing literature on COPD and stem cell treatment, and the anecdotes obtained

Rev\_2/5/16 Page 7 of 10

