### 13. RISK AND BENEFIT ANALYSIS

All measures are taken to minimize or mitigate risks to the patient. The following lists the potential risks as indicated on the patient informed consent:

- **Adverse reaction to stem cells** - There is a possibility of an adverse reaction to the application of stem cells. This risk is minimized by using autologous (your own) unaltered stem cells.
- **Anemia** - There have been reports of anemia with harvesting of stem cells from the circulation. This risk is low. To minimize this risk we request blood work (CBC).
- **Embolus development** - An embolus is a clot that may be from blood or cells such as fat or bone marrow. There is a chance that an embolus or emboli (plural) may develop with stem cell procedures. This risk is low and is minimized due to our stem cells processing protocols.
- **Failure of the procedure** - There is a chance that undergoing stem cell application will not alleviate symptoms, resolve inflammation, or assist in regenerating tissue.
- **Fever** - Fever associated with stem cell harvesting usually responds to acetaminophen. If fevers persist, a work-up for infection must be completed.
- **Infection** - Infection may occur at the donor site where the bone marrow or fat was harvested or at the IV site and recipient site of application. To minimize risk infection prevention protocols are maintained and followed during the treatment process and patient education is provided on post treatment cleaning and wound care.
- **Pain** - Any procedure can result in pain. To minimize this risk we ask that our patients communicate any discomfort so that we can reduce or mitigate.
- **Numbness/tingling** – Although a low risk, this has been reported with leukapheresis (the process of separating stem cells from peripheral blood in the vein). Laboratory analysis may be required along with calcium infusion.
- **Respiratory difficulties** - Breathing difficulties (which are usually temporary) or post-operative pneumonia, may occur as a result of any procedure or surgery. Pulmonary embolus, a blood clot causing blockage of an artery in the lungs may occur as a result of any procedure or surgery. Pulmonary embolus may be fatal.
- **Stroke** - Though a low risk and unlikely, there is a possibility that a stroke will occur during the procedure or in the recovery period.

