18.	
Clinic Staff gives Patient post-op instructions.
 
 
• Has Clinic Staff advised the Patient of the below post-op care instructions and ensured that they understand said instructions; answering any questions or concerns? 
 
✓ Practitioner made available to Patient for additional education and questions;
 
✓ Advised of no submerging of incision site in pools, hot tubs, bath, etc. for 7 days post-op;
 
✓ Advised to avoid excessive lifting and bending for the next seven days; and
 
✓ Advised to use ice as needed for 15 minutes per session for pain or swelling.
 
 
 
 
➤ If NO > Step must be completed prior to proceeding.
 
➤ If YES > Proceed to Step 19 of this SOP

19.	
Clinic Staff to review all discharge paperwork provided and answer any questions pertaining to treatment and discharge.
 
 
• Has Clinic Staff advised the Patient of the below post-care instructions and ensured that they understand said instructions; answering any questions or concerns? 
 
✓ Briefly review and explain the discharge folder contents to Patient;
 
✓ Review LI follow-up procedures; and
 
✓ Review Patient Journals for quality of life outcome data.
 
 
 
 
➤ If NO > Step must be completed prior to proceeding.
 
➤ If YES > Proceed to Step 20 of this SOP

20.	
Has Clinic Staff updated EMR as required?
 
 
• Capture procedure as required in the EMR: 
 
✓ Vitals
 
✓ Testing Conducted
 
✓ Medications Administered
 
✓ Lot Numbers and expirations (As Applicable);
 
✓ Dosage(s)
 
✓ Site(s) of Procedure and/or Administrations (Left vs Right, and location)
 
✓ Route (PO, SubQ, IM, IV, Etc.); and
 
✓ Any additional notation required.
 
 
 
 
➤ If NO > Step must be completed prior to moving forward.  ➤ If YES > Proceed to Step 21 of this SOP

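### Section 5b predicts no reported adverse events, which cannot answer the safety question, and the planned safety report has no stated denominator, interval or rule for patients not reached

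*Combined protocol and SAP*

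**What the plan says.** Section 5b, the only safety statement among the hypotheses in section 5, reads: "There will be no adverse events reported following autologous stem cell treatment for chronic lung disease". It names no grade, seriousness, relationship to treatment or period.

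Other places set a different expectation:

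- Section 1: "The hypothesized outcomes of Lung Institute therapy are safety and minimization of adverse events".
- Section 10: "The anticipated outcomes of this study are a minimization of adverse events".
- Section 13, among the risks: "Any procedure can result in pain".
- Discharge Treatment Day Procedure, step 18 (not reached on the venous path): "Advised to use ice as needed for 15 minutes per session for pain or swelling".

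On collection, section 11 has follow-up at "2 weeks, 3 months and 6 months post-treatment to measure adverse events and quality of life". It makes taking part in the calls voluntary and sends all adverse events to the Principal Investigator. Policy CL-005, part H, allows two attempts per contact. At six months it advises a return to the clinic or a local physician, and it describes the calls as a quality of life survey.

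On analysis, section 6 says: "Safety data on adverse outcomes will be tracked and reported separately as a descriptive, quantitative analysis". Section 12b describes sample characteristics, FEV1 values "evaluated by simple measures of central tendency (mean, median and mode") and the questionnaire. It does not mention adverse events. Section 12a anticipates 200 patients and does not name them as the safety denominator.

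**The concern.** Research question 1 in section 4 asks whether collection and administration are safe, and section 3 aims to confirm safety. Section 5b serves neither purpose, whichever way it turns out.

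- **If it is refuted**, the cause may be a single sore harvest site. The refutation would then carry no information about serious or treatment-related events.
- **If nothing is reported**, the result depends partly on who was reached, and a zero count still leaves a range of risks possible.

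What readers will use is the descriptive report promised in section 6. Without a denominator, an interval and a rule for patients not reached, they cannot tell how large a risk a low or zero count leaves open. Section 3 plans dissemination to the public and the medical community, so the safety statement will be read closely.

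**Working it through.** **Inputs.** The documents supply one number: 200 anticipated patients (section 12a). They give no adverse-event rate, margin, interval width or expected contact rate, so there is no safety calculation of the plan's own to reproduce. The per-patient risks p and the figure of 120 patients observed are assumptions, and patients are taken as independent.

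**Step 1. How easily is a zero-event prediction refuted?** With n patients observed, P(at least one patient with an event) = 1 − (1 − p)^n.

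| Assumed risk p | n = 200 | n = 120 |
|---|---|---|
| 0.1% | 18.1% | 11.3% |
| 0.5% | 63.3% | 45.2% |
| 1% | 86.6% | 70.1% |
| 2% | 98.2% | 91.1% |
| 5% | above 99.99% | 99.8% |

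For an 80% chance of no event in 200 patients, the risk would have to be 1 − 0.8^(1/200) = 0.11%. This is the risk of any event of any grade, because 5b sets no limit.

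**Step 2. What would zero reported events show?** The two-sided exact 95% upper limit after zero events is 1 − 0.025^(1/n).

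- n = 200: 1 − 0.025^(1/200) = 1.83%.
- n = 120: 1 − 0.025^(1/120) = 3.03%.

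The claim a zero count can support therefore depends on the denominator, which the plan does not state.

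**Step 3. Is an analysis stated elsewhere?** Section 6 says descriptive and separate. Section 12b covers FEV1 and the questionnaire. Policy CL-005, part E, points to OP-004 for reporting adverse occurrences. That policy is not in the text and is cited for reporting, not for analysis. No place gives a safety population, an interval or a rule for patients not reached.

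**Step 4. What would the repaired report look like?** Take 200 treated patients. Assume 6 with an event among those with a completed six-month contact, and 2 known from other sources among those without.

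- Minimum, all treated: (6 + 2)/200 = 4.0%, exact 95% CI 1.7% to 7.7%.
- Upper bound with 120 contacted: 80 are not contacted, of whom 78 have no known event, so (8 + 78)/200 = 43.0%.
- Upper bound with 160 contacted: 40 are not contacted, of whom 38 have no known event, so (8 + 38)/200 = 23.0%.
- Sensitivity, contacted only: 6/120 = 5.0% (1.9% to 10.6%), or 6/160 = 3.8% (1.4% to 8.0%).

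**The case against.** The strongest reply is that little depends on 5b. The study is descriptive and single-arm, and no test, success rule or stopping rule uses the hypothesis. All patients are treated, 200 are anticipated and the contact times are set, so all treated patients is the natural denominator. This limits the severity. It does not remove the gap, because a descriptive proportion still needs its denominator and precision stated, and voluntary calls make the choice matter.

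A second reply is that the passages do not contradict one another. Zero is the extreme case of minimization, section 13 lists possible risks, and the ice advice is given as needed and only off the venous path. This is correct: the mismatch is one of expectation, not of logic. Likewise, 5b is the only safety hypothesis within section 5, but section 1 also names safety as a hypothesized outcome.

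A third reply is that OP-004 may define events so as to leave out expected procedural discomfort. If it does, the claim that one mild event refutes 5b weakens. The text cannot settle this.

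A reader might also infer two stronger points that the documents do not support.

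- **That events in the clinic would usually decide 5b.** This needs an assumed in-clinic risk and a reading in which events during infusion count as following treatment. At an in-clinic risk of 0.1%, the chance of none in 200 patients is 0.999^200 = 81.9%.
- **That incomplete contact matters only when the later risk is about 2% or less.** This depends on assumed reach. At a later risk of 5%, the chance of none reported is 0.95^40 = 12.9% if 40 patients are reached, against 0.004% if all 200 are. The documents give no contact rate.

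**Conclusion.** The point holds in a limited form. Section 5b is a poor safety hypothesis: subject to OP-004, one mild event refutes it, and a count of zero leaves risks up to 1.8% (0/200) or 3.0% (0/120, assumed) compatible with the data. The consequential gap is in the report promised by section 6, which has no stated denominator, interval or handling of patients not reached. It should be changed, because research question 1 cannot be answered from 5b as written and the repair is small. The upper limits follow from the denominators alone; the refutation probabilities and the worked example rest on assumed risks, counts and reach.

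**What to change.** Replace 5b with an estimation objective and align sections 1 and 10 with it.

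- **Main figures.** Report the number and proportion of patients with any, any serious and any treatment-related adverse event from treatment through six months, among all treated patients. Count every known event from any source, whatever the contact status. Give exact 95% intervals and label the figures as minimums, because some patients will not be reached.
- **Beside them.** Show the numbers contacted and not contacted at 2 weeks, 3 months and 6 months, with an upper bound that adds every patient who has no known event and no completed six-month contact.
- **Sensitivity.** The proportion among patients with a completed six-month contact may be added. Nobody should enter that denominator because of their outcome. Adding known deaths while leaving out other known events in uncontacted patients, for example, would make inclusion depend on outcome.
- **Breakdown.** Report by procedure (venous, bone marrow) as well as overall.
- **Interpretation.** State that, with no control group (section 2a), any-event figures include events of the underlying lung disease. Read zero or low counts with their upper limit, not as proof of safety.
- **Collection.** Reconcile section 11 with CL-005, part H, so that the six-month contact asks about adverse events.

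The cost is one reworded hypothesis, one specified table, a contact log and IRB approval of the amendment; no visits or tests are added. The zero-event claim is given up, and the bounds may be wide if many patients are not reached. Relatedness must also be recorded for expected non-serious events, which goes beyond the IRB's list of reporting obligations.
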